3 STUDY OBJECTIVE

To collect confirmatory data supporting the safety and effectiveness of SSO₂ Therapy in the treatment of anterior acute myocardial infarction (AMI) patients who have undergone successful percutaneous coronary intervention (PCI) with stenting within six hours of experiencing AMI symptoms.

4 STUDY DESIGN

This is a non-randomized, single-arm study. Subjects who present with anterior STEMI requiring stent placement in the proximal and/or mid LAD who meet all inclusion and exclusion criteria and provide informed consent will be treated with primary PCI with stenting, and if successful and uncomplicated then immediately with post-procedure delivery of SSO₂ Therapy for a duration of 60 minutes.

4.1 Patient Enrollment

100 qualifying patients with anterior acute myocardial infarction will be enrolled into this study and treated with SSO₂ Therapy only after successful and uncomplicated revascularization of the LAD infarct artery.

4.2 Patient Follow-Up

Subjects will be followed clinically at baseline, procedural, in hospital, at 30-days (± 7 days; i.e., between 23 and 37 days), at 6-months (± 30 days) and at 12-months (± 30 days) following the index procedure. The clinical investigator or designee will conduct the 30-day follow-up assessment as an office visit, and the 6-month and 12-month follow-up assessments via telephone call. Patient adverse events will be tracked, monitored, and adjudicated through 12 months post-procedure. For the purpose of reporting study results, a clinical summary report will be issued after 30-day data are finalized and a supplementary report will be issued upon completion of 12-month assessments.

4.3 Cardiac Magnetic Resonance Imaging (MRI)

Patients will be evaluated with two cardiac MRI scans. The first scan will be conducted between day 3 and day 5 post-procedure (day 4 ± 1). The second scan will be conducted in conjunction with the mandatory 30-day clinical follow-up visit, on day 30 (± 7) post-procedure (between days 23-37). Every effort will be made to obtain the required MRI

scans, and scans obtained outside the protocol window will be reported. The necessary procedural details for conducting the cardiac MRI scans are provided in **Appendix E**.

Cardiac MRI images will be evaluated by the MRI Core Laboratory and the following information will be reported: microvascular obstruction (MVO) at day 3-5, infarct size at both imaging time points, and left ventricular volume at both imaging time points. Other standard MRI measures will also be reported at each time point.

4.4 Early Study Termination

No statistical rule for early termination is defined. However, TherOx, Inc. may discontinue the study at any stage with written notice to the investigators. Possible reasons for early termination may include identification of safety risks that pose an unreasonable risk to the patient. The independent Data Safety Monitoring Board will have responsibility for study oversight, including the timely review of critical safety events, and may make recommendations for study modification, suspension, or termination.

The study Executive Committee makes a final decision for early study termination. If the trial is terminated early, TherOx will provide a written statement describing why premature termination will occur, and notify the participating clinical investigators, investigational site IRBs, and FDA. All applicable clinical study documents will be subject to the same retention policy as detailed in **Section 10.10.1 Required Data**.

4.5 Measures Taken To Avoid / Minimize Bias

In order to minimize bias in assessing both effectiveness and safety data, the independent cardiac MRI Core Laboratory will evaluate patient scans independent of clinical outcome data, and an independent Clinical Events Committee (CEC) will be utilized for adverse event coding and relationships after review of original source documentation, blinded to the MRI results. An independent Data and Safety Monitoring Board (DSMB) will conduct reviews of overall study conduct and safety both during the enrollment period and at the conclusion of the study.

5 SSO₂ THERAPY PROCEDURAL AND SAFETY DATA

5.1 SSO₂ Therapy Procedural Data

Procedural information will be collected and reported for every patient treated with SSO₂ Therapy in this trial. The data collected and reported will include:

- SSO₂ Therapy device and infusion specifics
- Confirmation of stable delivery catheter position
- Intra-procedural hemodynamics
- Procedural complications, therapy interruptions or device shutdowns

5.2 Safety Data

All major adverse events will be evaluated and reviewed by an independent Clinical Events Committee (“CEC”). The following safety and procedural information will be reported and summarized:

- AEs and SAEs
- Adverse event relationships
- Intraprocedural complications
- Clinical, technical and procedural success

5.3 Number of Sites

Up to fifteen (15) centers located in the U.S.

5.4 Sample Size

One hundred (100) patients, non-randomized. All patients will receive a 60-minute SSO₂ Therapy infusion.

6 PATIENT SELECTION AND WITHDRAWAL

6.1 Patient Population

Patients must meet all of the study criteria outlined below in **Section 6.4.1** and **6.4.2** (reference Inclusion/Exclusion Criteria Case Report Form (CRF), **Appendix A**). No exclusion criteria outlined in **Section 6.4.2** may apply in order to be enrolled.

6.2 Patient Screening

All patients admitted to the emergency room or cardiac catheterization laboratory with symptoms \leq 6 hours after symptom onset and ECG findings suggestive of acute anterior AMI (ST-segment elevation of \geq 1 mm in 2 or more contiguous leads in V1-V4, or new left bundle-branch block), and who are considered potential candidates for percutaneous

revascularization with stenting, are potentially eligible for this protocol. All patients who meet clinical inclusion criteria should be documented (entered) on the site's study screening log. Thus, patients without ST-segment elevation and those with non-anterior MI or new left bundle branch block do not need to be recorded in the screening log. Reasons for screening failure will be noted in the final study report. If the potential study candidate has one or more clinical exclusion criteria present, or subsequently fails to meet angiographic selection criteria, the reason for screening failure must be entered on the screening log. A member of the research team should screen all eligible patients to determine eligibility and document any applicable reasons for non-enrollment on the screening log.

A signed Informed Consent must be obtained before cardiac catheterization begins, and before any study-related tests or procedures are undertaken.

6.3 Informed Consent

A member of the research team will approach the patient (or legal representative) to obtain written Informed Consent. The Informed Consent will be carefully explained to the patient. The patient (or legal representative) must sign the consent form approved by the Sponsor, FDA, and the study site's Institutional Review Board ("IRB"). The sample Informed Consent Form is attached as **Appendix B**. Signed Informed Consent Forms will be maintained at each investigational site.

6.4 Eligibility Criteria

6.4.1 Inclusion Criteria

Candidates for this study must meet **ALL** of the following criteria:

General Inclusion Criteria

Pre-PCI:

1. The subject must be ≥ 18 and ≤ 80 years of age.
2. AMI must be anterior (ST-segment elevation ≥ 1 mm in two or more contiguous leads between V1 and V4 or new left bundle branch block).
3. Subject is experiencing clinical symptoms consistent with acute MI of ≤ 6 hour duration from time of symptom onset until admission to the emergency room.

4. The subject or legally authorized representative has been informed of the nature of the study, agrees to its provisions and has been provided and signed written informed consent, approved by the appropriate Institutional Review Board (IRB).
5. Subject and his/her physician agree to all required follow-up procedures and visits.

ANGIOGRAPHIC INCLUSION CRITERIA: These are evaluated after the subject has provided signed Informed Consent but prior to enrollment:

6. Based on coronary anatomy, PCI is indicated for revascularization of the culprit lesion(s) with use of a commercially available coronary stent (bare metal or drug-eluting, at operator discretion) in the LAD.
7. The primary stented infarct-related lesion(s) must be in the proximal and/or mid-LAD coronary artery (other lesions in the LAD target vessel, including diagonal branches, may be treated if clinically indicated).
8. Baseline (pre-PCI) TIMI flow grade 0, 1, 2, or 3 flow in the LAD.
9. Successful angioplasty is completed ≤ 6 hrs from system onset, as documented by $<50\%$ diameter residual angiographic stenosis within all treated culprit lesions with TIMI 2 or 3 flow and no major complications such as perforation or shock.
10. Expected ability to place the SSO₂ delivery catheter in the coronary ostium of the left main coronary system to deliver SSO₂ Therapy with stable, coaxial alignment.

6.4.2 Exclusion Criteria

Subjects will be excluded if **ANY** of the following conditions apply:

General Exclusion Criteria

Pre-PCI:

1. Prior CABG surgery.
2. Prior myocardial infarction, or known prior systolic dysfunction (known ejection fraction $<40\%$ by any prior measure or regional wall motion abnormalities; this criterion does not include left ventricular dysfunction induced by the acute MI).
3. Thrombolytic therapy administered for this STEMI.
4. An elective surgical procedure is planned that would necessitate interruption of anti-platelet agents during the first 30 days post-enrollment.

5. Subjects who previously underwent coronary stent implantation and in whom coronary angiography demonstrates stent thrombosis to be the cause of the anterior AMI.
6. Subjects who have previously undergone an angioplasty or stenting procedure in the left anterior descending coronary artery.
7. Subjects with ventricular pseudoaneurysm, VSD, or severe mitral valve regurgitation (with or without papillary muscle rupture).
8. Any contraindication to MRI imaging. This will include any of the following exclusions:
 - a. Cardiac pacemaker or implantable defibrillator;
 - b. Non-MRI compatible aneurysm clip;
 - c. Neural Stimulator (i.e., TENS unit);
 - d. Any implanted or magnetically activated device (insulin pump);
 - e. Any type of non-MRI compatible ear implant;
 - f. Metal shavings in the orbits;
 - g. Any metallic foreign body, shrapnel, or bullet in a location which the physician feels would present a risk to the subject;
 - h. Any history indicating contraindication to MRI, including claustrophobia or allergy to gadolinium;
 - i. Inability to follow breath hold instructions or to maintain a breath hold for >15 seconds; and
 - j. Known hypersensitivity or contraindication to gadolinium contrast.
9. Known impaired renal function (creatinine clearance <30 ml/min/1.73 m² by the MDRD formula) or on dialysis.
10. Known platelet count <100,000 cells/mm³ or >700,000 cells/mm³ or a known Hgb <10 g/dL.
11. Subject has active bleeding or a history of bleeding diathesis or coagulopathy (including heparin induced thrombocytopenia), or refusal to receive blood transfusions if necessary.
12. History of intracerebral mass, aneurysm, arteriovenous malformation, or hemorrhagic stroke.
13. Stroke or transient ischemic attack within the past six (6) months, or any permanent neurological defect.

14. Gastrointestinal or genitourinary bleeding within the last two (2) months, or any major surgery (including CABG) within six weeks of enrollment.
15. Subject has received any organ transplant or is on a waiting list for any organ transplant.
16. Subject has other medical illness (e.g., cancer, dementia) or known history of substance abuse (alcohol, cocaine, heroin, etc.) that may cause non-compliance with the protocol, confound the data interpretation, or is associated with limited life expectancy of less than one year.
17. Subject has a known hypersensitivity or contraindication to unfractionated heparin, abciximab, aspirin, bivalirudin, cangrelor, clopidogrel, ticlopidine, prasugrel, eptifibatide, tirofiban or ticagrelor that cannot be adequately premeditated.
18. Current use of warfarin, dabigatran, or factor Xa inhibitors, or known intent to administer these agents after the primary PCI.
19. Subjects presenting with or developing in the cath lab prior to completion of the primary PCI procedure any of the following conditions: cardiogenic shock (SBP <80 mmHg for >30 minutes), or requiring IV pressors or emergent placement of an intra-aortic balloon pump (IABP), Impella, or other hemodynamic support for hypotension treatment, or cardiopulmonary resuscitation for >10 minutes, or ventricular fibrillation or tachycardia requiring cardioversion or defibrillation.
20. Severe known cardiac valvular stenosis or insufficiency, pericardial disease, or non-ischemic cardiomyopathy.
21. Any significant medical or social condition which in the investigator's opinion may interfere with the subject's participation in the study or ability to comply with follow-up procedures, including MRI (e.g. alcoholism, dementia, lives far from the research center, etc.).
22. Current participation in other investigational device or drug trials.
23. Previous enrollment in this study.

ANGIOGRAPHIC EXCLUSION CRITERIA: These are evaluated after the subject has provided signed Informed Consent but prior to enrollment:

24. Anticipated inability to achieve a stable coaxial position in the left main coronary artery with the SSO₂ delivery catheter.
25. Treatment during the index procedure of any lesion in either the left main, LCX (including the ramus), and/or RCA.

26. Post-index procedure planned intervention within 30 days (i.e., PCI of non-target lesions in any vessel, or CABG). Note: Planned revascularization (PCI or bypass) of a non-target lesion >30 days following the index procedure is allowed.
27. Anterior MI is due to thrombosis within or adjacent to a previously implanted stent.
28. Left ventriculography demonstrates severe mitral regurgitation, a ventricular septal defect, or a pseudoaneurysm.
29. Any left main coronary artery stenosis >20%.
30. Any untreated LAD or diagonal branch lesion is present with diameter stenosis \geq 50% in a vessel with reference vessel diameter > 2.0 mm (visually estimated), or for which PCI will be required before the MRI study.
31. Presence of a non-stented coronary dissection with NHLBI grade \geq B upon completion of the PCI procedure.

Subjects who meet the selection criteria will be enrolled into this multi-center clinical trial after successful screening and providing Informed Consent.

Please note: An Enrollment Notification Form should be completed and sent via facsimile to the study CRO after the procedure has been completed.

6.5 Patient Discontinuation

Once enrolled, each patient should remain in the study until the required follow-up period is complete. However, the patient has the right to withdraw from the study at any time. The following events will result in terminating the patient's follow-up:

- Patient death
- Patient voluntary withdrawal
- Patient withdrawn by investigator as clinically indicated
- Patient lost to follow-up (unofficial withdrawal)
- Study is terminated according to **Section 4.4** Early Study Termination

Appropriate case report forms must be completed for both study-terminated patients and patients who complete the entire follow-up. TherOx, Inc. must be notified of the reason of patient discontinuation. The site will provide this information on the appropriate case report form. Investigators must also report this information to their IRBs as defined by their institutions' procedures.

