Furthermore, the specific 30-day NACE event categories of death, stent thrombosis, myocardial rupture, and SAE bleeding will be examined in terms of individual events. The numbers provided in **Table 2** below represent the FDA-recommended 30-day event rate guidelines for these individual safety endpoints. FDA will conduct clinical review of event counts, severity, and patient circumstances. Events will be reviewed and evaluated in the context of individual patient circumstances, relationship to the investigational device, and overall patient status in an overall determination of device safety.

Table 2. FDA Guidelines for Acceptable Adverse Event Rates

30-Day MACE Event	IC-HOT Trial FDA Guideline
Death	$\leq 3.0\%$
Stent Thrombosis (definite)	$\leq 3.0\%$
Myocardial Rupture	$\leq 1.0\%$
TIMI Major and Minor Bleeding	$\leq 3.0\%$

Weighing the frequency, severity, and causal factors of the observed adverse events in this study, the safety profile of SSO₂ Therapy will be measured against the observed effectiveness results in an overall evaluation of the risk-benefit profile.

To further evaluate the safety profile of SSO₂ Therapy, the treatment cohort will be followed throughout the post-approval data collection period (12 months), however the primary endpoint will be at 30 days.

For the purpose of comparing the new, modified NACE endpoint for this confirmatory study with previous studies of SSO₂ Therapy, the data from the AMIHOT II study were re-examined using the new, modified NACE endpoint definitions. In total, 13.1% (29/222) of SSO₂ patients experienced 30-day NACE. Therefore, the IC-HOT clinical trial NACE endpoint OPG of 10.7% is more conservative than the AMIHOT II results.

In addition to 30-day NACE, the following data will also be reported and summarized:

- Additional bleeding events through 30 days, categorized by the BARC criteria
- All other 30-day adverse events
- Individual NACE component event rates through 1 year

Additional Study Endpoints

Effectiveness

Effectiveness is a secondary endpoint for this study. Effectiveness data from dual time point cardiac MRI scans at day 4 and day 30 will be collected and reported, using 30-day median infarct size (% left ventricle (LV) necrosis) as the primary effectiveness outcome

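### Terminating the study early, even for safety, ends protocol follow-up of patients already treated, so their outcomes after the stop would not be collected

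*Protocol*

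**What the plan says.** Protocol 6.5 begins with a general intention: "Once enrolled, each patient should remain in the study until the required follow-up period is complete". It then sets out exceptions under the words "The following events will result in terminating the patient's follow-up". The exceptions are death, voluntary withdrawal, withdrawal by the investigator, loss to follow-up and, last, "Study is terminated according to" section 4.4. The same section requires case report forms for patients whose participation ends this way.

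Protocol 4.4 states "No statistical rule for early termination is defined" and lets the sponsor stop at any stage. On grounds it says: "Possible reasons for early termination may include identification of safety risks that pose an unreasonable risk to the patient". The Executive Committee takes the final decision. On what must then happen, "TherOx will provide a written statement describing why premature termination will occur"; investigators, IRBs and FDA are notified, and the record retention policy applies. Follow-up of patients already treated is not mentioned.

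Elsewhere the schedule is stated without reference to early termination. Protocol 4.2 says "Patient adverse events will be tracked, monitored, and adjudicated through 12 months post-procedure". Protocol 8.3 extends adverse event reporting to all subjects over the same 12 months. Protocol 9.2 says "the treatment cohort will be followed throughout the post-approval data collection period (12 months"), with the primary endpoint at 30 days.

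Protocol 8.7 separately allows the DSMB to advise ending or suspending enrollment. SAP 5.2 times the primary analysis for when every patient has completed the 30-day assessment. It has no provision for a study that ends early.

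**The concern.** For a drug taken daily, ending the study also ends the exposure. Here exposure is one infusion lasting 60 minutes. A safety termination protects people not yet enrolled; those already infused still carry whatever risk prompted the stop. Section 6.5, read literally, removes the planned 30-day visit and the 6- and 12-month calls from exactly those patients.

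The guideline rates in Protocol 9.2 are sensitive to single events. With 50 patients treated, one event is 1/50 = 2% and two are 2/50 = 4%. The guideline is 1.0% for myocardial rupture and 3.0% each for death, definite stent thrombosis and TIMI bleeding. One uncaptured event after the stop could therefore change how a component compares with its guideline in any later review. Component rates through 1 year, which the plan promises to report, would lose most of their data.

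**Working it through.** The plan gives no figure on this point, so there is nothing to reproduce. The check is of the text first, then of scale under stated assumptions.

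**Text**

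1. Is the rule mandatory? Yes. Section 6.5 says the listed events will end follow-up, with no qualifier.
2. Does it reach safety stops? Yes. The bullet points to 4.4, and 4.4 offers safety risk as a reason.
3. Does 4.4 restore follow-up? No. It asks for a statement, notifications and retention of records.
4. Does anything else restore it? Sections 4.2, 8.3 and 9.2 give the 12-month schedule but do not say it survives termination. SAP 5.2 and 6.2 do not address it.
5. What is kept? Data before the stop: 6.5 requires the forms, and 9.1 and 9.2 include all available data.
6. What does not trigger the rule? Ending or suspending enrollment (8.7). Section 4.4 likewise lists modification, suspension and termination as separate options; only termination appears in 6.5.

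**Scale**

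Inputs: 100 patients (Protocol 5.4). The accrual period is not given, so 6, 12 and 24 months are assumed, with even accrual.

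Patients short of a follow-up length at the stop = smaller of (number enrolled) and (monthly accrual rate × follow-up length in months). Thirty days is 30/30.4375 = 0.986 months.

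| Assumed accrual | Rate per month | Short of 30 days | Short of 12 months, stop at 50 | Short of 12 months, stop at 100 |
|---|---|---|---|---|
| 6 months | 100/6 = 16.7 | 16.4 | 50 | 100 |
| 12 months | 100/12 = 8.3 | 8.2 | 50 | 100 |
| 24 months | 100/24 = 4.2 | 4.1 | 50 | 50 |

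The 30-day column applies to any stop during enrollment after its first 30 days. For a stop at 50 treated, it is 33%, 16% or 8% of them.

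These patients are partly observed. Under even accrual they average 15 of 30 days. For a stop at 50, the 30-day patient-time lost is 8.2 × 15 = 123 of 50 × 30 = 1,500 patient-days (8.2%) with 12-month accrual, and 4.1 × 15 = 61.5 of 1,500 (4.1%) with 24-month accrual.

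Later follow-up suffers more. A stop at 50 comes at month 6 or month 12 of accrual respectively, so mean observed time is 3 or 6 months of the planned 12. The loss is 9/12 = 75% or 6/12 = 50% of planned 12-month patient-time.

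**The case against.** The strongest reply is that this is a contingent drafting gap. It matters only if the Executive Committee ends the whole study instead of stopping enrollment, and the second route is already available and leaves follow-up running. That limits how often the rule would bite. It does not remove the rule, because 4.4 permits full termination at any stage.

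Several stronger readings are tempting, and the documents do not support them:

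- A reader might infer that any safety action cuts follow-up. Only termination does.
- A reader might infer a flat contradiction between 6.5 and sections 4.2 and 9.2. Those sections set a default schedule and 6.5 lists exceptions to it, just as withdrawal is an exception. Section 8.3, with its reference to all subjects, comes closest to a conflict, and the texts should be reconciled.
- A reader might infer that a safety signal could not be sized, or that every patient inside 30 days loses the primary endpoint. Events before the stop are kept, and the visit window opens at day 23, so some will have been seen.
- A reader might infer that the DSMB would advise on truncated data. Its recommendation comes before the stop; the loss affects review afterwards.
- A reader might infer that the observed NACE rate would be pulled below the 10.7% goal. Take AMIHOT II's 13.1% as the true rate, 50 treated, and truncated patients left in the denominator with no events captured. The rate would read 13.1% × 42/50 = 11.0% with 8 truncated, or 13.1% × 34/50 = 8.9% with 16. Only the second is below the goal. It needs 6-month accrual and ignores every event before the stop. SAP 6.2 also provides for sensitivity analyses of missing data.

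The rule also does not touch clinical care: what ends is protocol surveillance. The DSMB charter, the consent form and the close-out procedure mentioned in Protocol 10.8.3 were not available and might address the matter.

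**Conclusion.** The point holds as a stated rule with a poor consequence. If the study is terminated under 4.4, including for safety, the protocol ends follow-up of patients already treated, and no available text preserves it. Only outcomes after the stop are lost. A study that runs to completion is unaffected.

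The size cannot be derived from the documents. With even accrual over 12 to 24 months (an assumption), about 4 to 8 patients would have an incomplete 30-day window. For a stop at 50 treated, all 50 would lack complete 12-month follow-up. The text conclusion does not depend on these figures. The change is worth making because it is cheap and cannot easily be made once a stop is under way.

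**What to change.** 1. **Protocol 6.5:** remove the study-termination bullet, or qualify it by reference to the new text in 4.4.
2. **Protocol 4.4:** state that early termination, at least when it is for safety, ends enrollment, while patients already enrolled continue the planned 30-day, 6-month and 12-month safety contacts with CEC adjudication. The other exits in 6.5 (death, patient withdrawal, investigator withdrawal, loss to follow-up) stay in force.
3. **Protocol 4.2 and 8.3:** reconcile with the revised 6.5, so that sites read one rule on how long adverse events are collected after a stop.
4. **SAP 5.2:** add that, if the study is terminated early, the primary analysis is done once all enrolled patients have reached 30 days or left the study.

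The cost is a few sentences in an amendment. If the study does stop early, the sponsor funds contacts and adjudication that were already planned, for up to 12 months. Limiting the commitment to safety terminations would reduce that cost where the stop has another cause.
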